#### 4.1.2 Exclusion criteria

- No decision to conduct full life support
- No written informed consent
- Congenital malformation

#### 4.1.3 Patient groups

1. Preterm neonates (<37+0 weeks of gestation)

## 2. Term neonates ( $\geq 37+0$ weeks of gestation)

## 5 Sample size

In preterm infants, it was found that the correlation between MABP, and cFTOE is  $r = -0.19$  at 15 minutes after birth. Even lower correlations were found for crS02 and MABP and for term infants (38). Due to the bevor in 1.6. described changes during the immediate transition period, which lead to a decrease in cardiac preload and an increase in cardiac afterload the cardiac output is reduced. Considering these changes in the cerebral blood flow as well as the systemic blood flow and systemic blood pressure we expect to find higher correlations in the fifth and tenth minute after birth. According to our experience, it is feasible to include 50 infants in this study. If 50 infants are included and a drop-out rate of 10% is considered, 45 infants can be analyzed. Using these 45 infants the lower limit of Spearman's rank correlation coefficient's 95% CI will be 0.14 for a correlation coefficient of  $r = 0.40$ . This lower limit increases to 0.20, 0.26, 0.32 for  $r = .45$ ,  $r = .50$  and  $r = .55$  respectively.

Therefore we aim for a sample size of 50 neonates in each group – preterm neonates and term neonates, resulting in a total sample size of 100 neonates

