## 14 Data analysis

Initially, all data will undergo a descriptive analysis to uncover any data anomalies and missing values that may impact the validity of the data analysis.

Demographic, NIRS and routine monitoring data will be presented as n (%), mean and standard deviation (SD), or median and interquartile range (IQR), as appropriate.

Comparisons of categorical characteristics between preterm and term infants will be performed using chi-square test and for continuous variables using t-test or Mann-Whitney U-test, as appropriate.

Correlation analyses will be performed to investigate, if there is a connection between crSO2, cFTOE and MAP in preterm and term infants at different time points, individually. Correlations will be performed using Spearman's rank correlation coefficient or Pearson's correlation when appropriate. A p-value < 0.05 will be considered statistical significant. The statistical analyses will be performed using IBM SPSS Statistics 22.0.0 (IBM Corporation; Armonk, USA).

Comparison of correlation analyses at different time points and in term and preterm neonates will be descriptive. Statistical analysis is planned to be performed in cooperation with the Institute for Medical Informatics, Statistics and Documentation, Medical University of Graz, Austria.

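### The lower confidence limits in section 5 do not hold for 45 infants and Spearman's coefficient; they match a Pearson-type interval for 50

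*Combined protocol and SAP*

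**What the plan says.** Section 5 (Sample size) starts from feasibility: 50 infants can be recruited. It then allows for losses: "If 50 infants are included and a drop-out rate of 10% is considered, 45 infants can be analyzed". The precision statement is tied to that reduced number: "Using these 45 infants the lower limit of Spearman's rank correlation coefficient's 95% CI will be 0.14 for a correlation coefficient of" r = 0.40. It goes on: "This lower limit increases to 0.20, 0.26, 0.32 for" r = 0.45, 0.50 and 0.55. The conclusion follows directly: "Therefore we aim for a sample size of 50 neonates in each group", one group preterm and one term, 100 in total.

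Section 5 gives no formula or software for the interval. Section 14 (Data analysis) adds: "Correlations will be performed using Spearman's rank correlation coefficient or Pearson's correlation when appropriate". Its criterion for a finding is "A p-value < 0.05 will be considered statistical significant". It does not mention confidence intervals for the correlations.

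**The concern.** The sentence fixes everything needed to check it: the number analysed (45), the coefficient (Spearman), the confidence level (95%) and four pairs of coefficient and limit. The printed limits look too high for 45 infants.

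The plan contains no power calculation, so these four limits are all the statistical support it offers for its size. If they belong to 50 infants, the text tells the reader that attrition has been allowed for when the numbers do not allow for it. The intervals in each group would then be wider than planned. This matters more because the only earlier correlation that section 5 quotes is weak (r = −0.19 at 15 minutes in preterm infants, with lower values elsewhere), and the case for the study rests on finding clearly stronger ones.

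**Working it through.** **Inputs, all from section 5.** Enrolled per group: 50. Drop-out: 10%, so 50 × 0.90 = 45 analysed. Confidence level: 95%, taken as two-sided (z = 1.96). Coefficients: 0.40, 0.45, 0.50, 0.55. Printed lower limits: 0.14, 0.20, 0.26, 0.32.

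**Formula.** Lower limit = tanh(atanh(r) − 1.96 × SE), where SE² is one of:

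- plain Fisher z (Pearson): 1/(n−3)
- Spearman, Fieller: 1.06/(n−3)
- Spearman, Bonett–Wright: (1 + r²/2)/(n−3)
- Spearman, Caruso–Cliff: 1/(n−2) + |z|/(6n + 4√n), with z = atanh(r)

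**Step 1: reproduce the printed figures.** Plain Fisher z with n = 50 gives 1.96/√47 = 0.2859. At r = 0.40, atanh(0.40) = 0.4236, and tanh(0.4236 − 0.2859) = 0.137. The other three limits are 0.196, 0.257 and 0.321. Rounded, these are 0.14, 0.20, 0.26 and 0.32, which is the printed set.

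**Step 2: the same calculation with the stated n = 45.**

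- Plain: 1.96/√42 = 0.3024; at r = 0.40, tanh(0.4236 − 0.3024) = 0.121.
- Fieller: 1.96 × √(1.06/42) = 0.3114; at r = 0.40, tanh(0.4236 − 0.3114) = 0.112.

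| Interval | n | r = 0.40 | r = 0.45 | r = 0.50 | r = 0.55 |
|---|---|---|---|---|---|
| Printed in section 5 | 45 (stated) | 0.14 | 0.20 | 0.26 | 0.32 |
| Plain Fisher z | 50 | 0.137 | 0.196 | 0.257 | 0.321 |
| Plain Fisher z | 45 | 0.121 | 0.180 | 0.242 | 0.306 |
| Spearman, Fieller | 45 | 0.112 | 0.172 | 0.234 | 0.298 |
| Spearman, Bonett–Wright | 45 | 0.109 | 0.166 | 0.225 | 0.286 |
| Spearman, Caruso–Cliff | 45 | 0.115 | 0.174 | 0.234 | 0.297 |
| Spearman, Fieller | 50 | 0.129 | 0.188 | 0.250 | 0.313 |

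**Step 3: look for another explanation.**

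- One-sided 95% limits at n = 45 are too high (plain: 0.168, 0.227, 0.287, 0.349).
- Spearman intervals at n = 50 do not match either.
- Scanning n from 30 to 119 with SE² = 1/(n−3), only n = 50 and n = 51 match all four figures.
- With a Spearman variance, a match needs 52 to 56 analysed infants: Caruso–Cliff 52–54, Fieller 53–54, Bonett–Wright 55–56.
- The only match found at n = 45 combines SE² = 1/n with an upward bias shift, which is not a recognised interval.

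**Step 4: size of the discrepancy (printed minus recomputed at n = 45).** Plain Fisher z: 0.014 to 0.020. Fieller: 0.022 to 0.028. Bonett–Wright: 0.031 to 0.035. Rounding to two decimals can account for at most 0.005. In relative terms the Fieller gap is (0.14 − 0.112)/0.14 = 20% at r = 0.40, falling to (0.32 − 0.298)/0.32 = 7% at r = 0.55.

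**Step 5: smallest coefficient whose interval excludes zero.** Plain, n = 50: tanh(0.2859) = 0.28. Plain, n = 45: tanh(0.3024) = 0.29. Fieller, n = 45: tanh(0.3114) = 0.30.

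**The case against.** The strongest reply is that the error changes no decision. Section 5 sets the number by feasibility and fixes no target width, minimum limit or power, so no planning criterion is missed. Section 6 calls this an observational pilot study. Every recomputed limit is above zero (lowest 0.109). The interval at r = 0.40 is already about 0.50 wide, so a shift of 0.02 to 0.03 is modest. All of this stands, and it limits how serious the point is. It does not make the printed figures right, and section 5 does draw its conclusion of 50 per group straight from them.

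A second reply is that the cause is inferred. This also stands: with no formula given, n = 50 with 1/(n−3) is the best explanation, not a documented one. It is a strong inference, because 50 is the enrolment before drop-out and all four figures match. That the limits are wrong for 45 infants does not depend on it.

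A third reply is that the Spearman variance is a choice among approximations, and that section 14 also allows Pearson. That is fair, and it is why the two effects are kept apart above. The formula most favourable to the plan still gives 0.12, 0.18, 0.24 and 0.31 at n = 45, so the discrepancy survives whichever coefficient is used.

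**Conclusion.** The concern holds. The four lower limits in section 5 are not those of a 95% interval with 45 infants, whether for Spearman or for Pearson. They agree with a plain Pearson-type Fisher z interval for 50 infants, the number before drop-out. The overstatement is about 0.014 to 0.020 from the sample size alone and about 0.022 to 0.035 once a Spearman variance is also used. The smallest correlation distinguishable from zero is about 0.30 rather than about 0.28.

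This assumes a two-sided 95% interval and one of the usual large-sample formulas. The error is small and does not invalidate the design. It should still be corrected, because an explicit precision claim, the plan's only statistical argument for its size, is not what the stated design delivers.

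**What to change.** Keep 50 infants per group. In section 5, restate the limits for 45 analysed infants and name the interval: Fisher z with Spearman variance 1.06/(n−3), giving lower limits of 0.11, 0.17, 0.23 and 0.30 for r = 0.40, 0.45, 0.50 and 0.55. Another recognised Spearman variance would serve equally well, provided it is named and its own limits are printed. Add that the smallest coefficient whose interval excludes zero is about 0.30.

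In section 14, state that each correlation will be reported with the same type of 95% interval. The arithmetic error does not by itself require this, but a sample size argued from precision calls for it.

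The cost is a corrected sentence in section 5 and one line in section 14, with a slightly less favourable precision statement and no additional infants. The alternative, keeping the printed limits with a Spearman interval, would need about 52 to 56 analysed infants per group. At 10% drop-out that is 52/0.90 to 56/0.90, or about 58 to 63 enrolled per group. Since feasibility set the number at 50, correcting the text is the simpler course.

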## 6 Study design

Prospective observational pilot study

## 7 Monitoring

### 7.1 Routine Monitoring

$\text{SpO}_2$ , heart rate, and central temperature will be monitored routinely. In addition, if CPAP or PPV are required non-invasive respiratory-function monitoring and transcutaneous  $\text{pCO}_2$  as routine non-invasive monitoring will be performed in the first minutes of resuscitation.

#### Routine monitoring:

- 1) Pulse oximetry (MR7CDS1 Radical 7, Chemomedica, Austria / IntelliVue MP70, Philips, Netherland)
- 2) Peripheral and central temperature (IntelliVue MP70, Philips, Netherland)
- 3) Respiratory function monitor (Monivent)
- 4)  $\text{pCO}_2$  (TC Sensor 84, etC02 Sensor, Radiometer RSCH GmbH, Thalwil, Switzerland / IntelliVue MP70, Philips, Netherland)

## 7.2 Additional Monitoring

In addition during the first 15 minutes we will record: NIRS measurements, non-invasive blood pressure and cardiac output.

### Additional Monitoring:

- 5) NIRS (t-NIRS, Hamamatsu, Japan)
- 6) Blood pressure measurement (IntelliVue MP70, Philips, Netherland)
- 7) Cardiac Output (Aesculon-EV-Monitor, Osypka, Berlin, Germany)

### 7.3 NIRS - cerebral regional oxygen saturation- tissue oxygenation index

For NIRS measurements the t-NIRS device (Hamamatsu, Japan ) will be used. This monitor uses a “time resolved” technique and measures non-invasively oxygenated, deoxygenated and total hemoglobin and tissue oxygenation index (TOI that corresponds to cerebral regional oxygen saturation).

Immediately after birth when the neonate is brought to the resuscitation desk, a sensor will be placed and fixed with a CPAP cap on the left forehead.

### 7.4 Blood pressure

For non-invasive blood pressure measurements the IntelliVue MP50 monitor (Philips, Netherland) will be used. The pneumatic cuff will be placed around the left upper arm and blood pressure measurements will be performed during the first fifteen minutes after birth.

### 7.5 Cardiac output Monitoring

For non-invasive cardiac-output measurements the Aesculon-Monitor (Osypka, Berlin, Germany) will be used. The monitor uses a new technique of thoracic bioimpedance. Four surface EKG electrodes are placed over the skin (forehead, left side of the neck, left hemithorax and left thigh).

## 8 Routine Interventions

Resuscitation will be according the “European Consensus Guidelines” on the management of neonatal respiratory distress syndrome (2).

## 9 Outcome measures

### 9.1 Primary

- Blood pressure minute 5, 10 and 15
- NIRS data measured with t-NIRS minute 5, 10 and 15
- FTOE minute 5, 10 and 15

### 9.2 Secondary

- Cardiac output minute 5,10 and 15
- Gestational age

### 9.3 Exploratory

- Respiratory support during resuscitation
- SpO2 level at each minute
- HR level at each minute
- Temperature minute 5 and 15
- Monitoring parameters during the first 15minutes after birth:
  - Mean (SD) HR
  - Mean (SD) BP

### 10 Outcome assessment tools

- Monitoring during the first 15 minutes after birth
- Medical history
- Severe morbidities and all cause mortality will be recorded

### 11 Risks and benefits

Pulse oxymetry the recommended routine monitoring will be performed in all neonates and SpO2 will be kept within normal ranges (10th-90th centile) (2) in all neoantes hypoxogenation and hyperoxogenation defined by the routine monitoring should be avoided. Blood measurements are routine in neonates in the NICU and well tolerated. Irritation of the skin due to the NIRS and the Aesculon-Monitor sensors is improbable, because of the short measurement period. Risks related to the manipulation of the patient during positing and repositing of the sensors will be minimized by experience of research team. Neonates will always be under routine monitoring and observation by nurses and neonatologists.

### 12 Informed consent procedure

Parents of potential participants will be invited to enroll their preterm newborn, when possible, before delivery. The qualified physician will make contact and parents will be informed of the study and given the Parent information sheet. The parents will be given time to think and ask

questions, before a written informed consent can be obtained. Parents will be given a copy of the informed consent.

## 13 Data collection

NIRS data and other monitoring data (SpO2, HR, tcpCO2, and temperature) will be collected in a polygraphic system (alpha-trace digital MM, B.E.S.T. Medical Systems, Austria). Blood pressure, demographic and medical history data will be anonymized and collected with a CRF.

## 14 Data analysis

Initially, all data will undergo a descriptive analysis to uncover any data anomalies and missing values that may impact the validity of the data analysis.

Demographic, NIRS and routine monitoring data will be presented as n (%), mean and standard deviation (SD), or median and interquartile range (IQR), as appropriate.

Comparisons of categorical characteristics between preterm and term infants will be performed using chi-square test and for continuous variables using t-test or Mann-Whitney U-test, as appropriate.

Correlation analyses will be performed to investigate, if there is a connection between crSO2, cFTOE and MAP in preterm and term infants at different time points, individually. Correlations will be performed using Spearman's rank correlation coefficient or Pearson's correlation when appropriate. A p-value < 0.05 will be considered statistical significant. The statistical analyses will be performed using IBM SPSS Statistics 22.0.0 (IBM Corporation; Armonk, USA).

Comparison of correlation analyses at different time points and in term and preterm neonates will be descriptive. Statistical analysis is planned to be performed in cooperation with the Institute for Medical Informatics, Statistics and Documentation, Medical University of Graz, Austria.

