### 1.6 Physiological changes of the cardio—circulatory system during transition

The main difference of fetal cardio-circulation to the cardio-circulation after birth is that before birth the lungs are by-passed, and the oxygenated blood is provided by the placenta. The three bypasses are the ductus venosus (DV), a connection between the umbilical vein and the vena cava inferior, the ductus arteriosus (DA), a vessel between pulmonary artery and the aorta to avoid pulmonary circulation, and the foramen ovale (FO), a connection between the cardiac atria which also serves the purpose to bypass the pulmonary circulation.

Due to these described peculiarities the fetal circulation is a parallel circulation instead of a serial one (32, 33).

During transition, the pulmonary resistance drops, due to the lung aeration. This resistance-drop triggers an increase of the pulmonary blood-flow. Considering this new detour, depending on when the umbilical cord was clamped, the preload is reduced during the first minutes after birth. Furthermore, due to the cord clamping the low-resistance placenta circulation is yield, which leads to an increased afterload and the arterial pressure increases. As a result of reduced preload and initial-increased afterload, the cardiac output is reduced with clamping the cord.

Considering these changes, the cerebral blood-flow as well as the systemic blood flow and systemic blood pressure are initially increased whereby a drop occurs immediately after the initial increase due to the reduced cardiac output (34). Afterwards, the cardiac output continues to stay low until the pulmonary blood-flow increases with ventilation of the lungs (35). During this cardio-circulatory and pulmonary changes immediately after birth the cerebral autoregulatory mechanisms should maintain the cerebral blood-flow constant. These autoregulatory mechanisms are not yet fully comprehensible especially in preterm neonates (36, 37).

In term neonates Baik et al have demonstrated that cFTOE as well as crSO2 are independent of MABP (38, 39). However, Baik's study (38) only investigated MABP in connection with crSO2 as well as cFTOE 15 minutes after birth. However, the question remains, if in term neonates MABP has some influence on cerebral oxygenation before minute 15 after birth when the lung is aerated, and most cardio-circulatory changes take place.

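### The sample size rests on 95% confidence limits for the correlations, but section 14 plans only p < 0.05 and a descriptive group comparison; intervals for each correlation and each group difference should be planned

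*Combined protocol and SAP*

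**What the plan says.** Section 5 (Sample size) plans on precision. It allows for dropout, "If 50 infants are included and a drop-out rate of 10% is considered, 45 infants can be analyzed", and then states that "the lower limit of Spearman's rank correlation coefficient's 95% CI will be 0.14" when the coefficient is 0.40. It continues: "This lower limit increases to 0.20, 0.26, 0.32 for" coefficients of 0.45, 0.50 and 0.55. On that basis "we aim for a sample size of 50 neonates in each group". It names no power and no hypothesis test.

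Section 14 (Data analysis) plans Spearman or Pearson correlations of crSO2 and cFTOE with mean arterial pressure, separately by group and time point. Its one inferential rule is "A p-value < 0.05 will be considered statistical significant". No confidence interval for a correlation is mentioned. On contrasts it says: "Comparison of correlation analyses at different time points and in term and preterm neonates will be descriptive".

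Differences between term and preterm neonates are nevertheless a secondary aim (section 2.2), and section 3.2 expects the cardiac-output correlations to be stronger in preterm neonates. In describing earlier work in term neonates, section 1.6 says that "cFTOE as well as crSO 2 are independent of MABP".

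**The concern.** The quantity used to justify the sample size is not a planned result. A reader of the final report would get coefficients and p-values but could not see which correlations the data still allow.

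This matters in two ways. First, with 45 infants per group a moderate true correlation can easily miss p < 0.05, and without an interval such a result may be taken as absence of influence or as intact autoregulation. Second, if a correlation is significant in preterm and not in term neonates, comparison by eye may turn that pattern into a group difference that the data do not support. Section 1.6 uses wording of both kinds about earlier results: it calls the term result independence, and it contrasts that with a significant preterm correlation to suggest less mature autoregulation and a possible benefit of blood pressure monitoring.

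**Working it through.** **Inputs.** From section 5: 50 enrolled and 10% dropout, so 50 × 0.9 = 45 analysed per group; planning values r = 0.40, 0.45, 0.50 and 0.55; earlier correlation r = -0.19 (MABP with cFTOE, preterm, minute 15). From section 14: significance level 0.05. Assumptions: two-sided testing (not stated), independent infants, and the Fisher z approximation. Sizes are given as |r|; for cFTOE the signs reverse.

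**1. The plan's own figures.** Lower limit = tanh(atanh(r) − 1.96/√(n − 3)).

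| r | Section 5 | n = 45 | n = 50 |
|---|---|---|---|
| 0.40 | 0.14 | 0.121 | 0.137 |
| 0.45 | 0.20 | 0.180 | 0.196 |
| 0.50 | 0.26 | 0.242 | 0.257 |
| 0.55 | 0.32 | 0.306 | 0.321 |

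The stated limits match 50 infants, not the 45 they are said to describe. The gap is about 0.02 and is a separate matter; the calculations below use 45.

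**2. What p < 0.05 requires.** SE = 1/√42 = 0.1543, and 1.96 × 0.1543 = 0.302. The smallest significant coefficient is tanh(0.302) = 0.294.

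**3. Power per correlation.** Power ≈ Φ(atanh(r)/0.1543 − 1.96); the opposite tail is negligible.

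| True r | atanh(r)/SE | Power | Non-significant |
|---|---|---|---|
| 0.19 | 1.246 | 24% | 76% |
| 0.30 | 2.006 | 52% | 48% |
| 0.40 | 2.746 | 78% | 22% |
| 0.50 | 3.560 | 95% | 5% |

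With a variance of 1.06/(n − 3), one of the forms used for Spearman's coefficient, power is slightly lower: 23%, 50%, 76% and 93%.

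**4. What a non-significant result leaves open (n = 45).**

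| Observed r | 95% CI |
|---|---|
| 0 | -0.29 to 0.29 |
| 0.10 | -0.20 to 0.38 |
| 0.19 | -0.11 to 0.46 |

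Even an observed r of 0 does not exclude 0.19, the correlation that section 5 cites.

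**5. Significant in one group only.** Suppose both true correlations are 0.30 (an illustrative value). Each group is significant with probability 0.518, so exactly one is significant with probability 2 × 0.518 × 0.482 = 0.50, with no true difference at all.

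**6. Precision of a group contrast.** On the z scale the SE of a difference is √(2/42) = 0.218. Combining the two groups' separate limits, illustrative coefficients of 0.35 (p = 0.018) and 0.20 (p = 0.19) differ by 0.15, with a 95% CI of -0.25 to 0.54 (Bonett-Wright variance). One is significant and the other is not, yet the interval for the difference spans zero widely. Power to separate true correlations of 0.40 and 0.19 is about 18%, and of 0.40 and 0 about 49%.

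**The case against.** The strongest reply is that the plan makes no negative claim. Primary Hypothesis I is that a correlation exists in both groups, and no section says that a non-significant result will be read as no influence. A reader might infer such a rule from the wording in section 1.6. The documents do not support that: the sentence summarises an earlier publication, and the section then leaves the question open for the time before minute 15. The risk of misreading is plausible but not written into the plan.

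Nor does the plan offer p-values alone. The coefficients are themselves the planned analysis, and what is missing is their interval. A descriptive comparison of groups is openly declared and legitimate in a pilot study; the primary hypothesis claims no group difference.

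The value 0.19 is also a minute-15 preterm figure. Section 5 expects stronger correlations at minutes 5 and 10, and at 0.40 or 0.50 far fewer results would be non-significant. This is why the whole range is shown above.

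All of this stands, and it limits the point to what section 14 should report and how it should be read. It does not remove the mismatch. A coefficient without an interval hides what the data still allow, a pilot study is where estimates with their precision are most useful, and a difference with a CI is compatible with a descriptive comparison.

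**Conclusion.** The point holds as a mismatch between sections 5 and 14: the study is sized on intervals that the analysis does not plan to report. With 45 infants per group, a non-significant correlation cannot show absence of influence, and significance in one group only does not show a group difference. The size depends on the true correlation, with between 76% (r = 0.19) and 5% (r = 0.50) of results non-significant. These figures rest on a two-sided test, independent infants, the Fisher z approximation and 45 analysed infants at every time point. The value of 0.30 in both groups and the contrast of 0.35 with 0.20 are illustrations, not forecasts. The conclusion does not extend to saying that the investigators will misread their results.

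**What to change.** Add to section 14:

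- Each primary correlation (crSO2 and cFTOE with MABP, at minutes 5, 10 and 15, in each group: 2 × 3 × 2 = 12) is reported with a 95% CI. Use a Fisher z interval, with a variance suited to Spearman's coefficient where Spearman is used.
- The preterm-minus-term difference in correlation is reported with a 95% CI for each measure and minute (2 × 3 = 6).
- The cardiac-output correlations and their group differences are reported in the same way, labelled exploratory.
- A non-significant correlation is not evidence of no influence, and group differences are judged from the CI of the difference, not by comparing p-values.

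It would be tempting to add a rule that declares no relevant association when the CI lies inside ±0.40, the smallest planning value in section 5. This should not be adopted. Section 5 uses 0.40 only to illustrate precision and nowhere calls smaller correlations irrelevant. With 45 infants the rule is met when |r| is below tanh(0.424 − 0.302) = 0.12, which happens in about 30% of studies if the true r is 0.19 and about 11% if it is 0.30.

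The cost is a few sentences and a little more analysis, with no extra infants, procedures or data. The drawback is that more results will be described as inconclusive.

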### 3.2 Secondary Hypotheses II

Cardiac output correlates with cerebral oxygen saturation and cerebral fractional oxygen extraction, whereby higher cardiac output is associated with higher cerebral oxygen saturation and lower cerebral fractional oxygen extraction, whereby correlations are more pronounced in preterm neonates within the first 15 minutes after birth.

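### Secondary Hypothesis II expects stronger cardiac-output correlations in preterm neonates, but section 14 plans no estimate or interval for that group difference

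*Combined protocol and SAP*

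**What the plan says.** Section 3.2 states Secondary Hypothesis II. Its main clause is that higher cardiac output goes with higher cerebral oxygen saturation and lower extraction. A subordinate clause ranks the groups: "whereby correlations are more pronounced in preterm neonates within the first 15 minutes after birth". The clause does not name its comparator, but section 2.2 makes term/preterm differences a secondary aim and section 4.1.3 defines only those two groups, so term neonates are the natural reading. Section 9.2 lists "Cardiac output minute 5,10 and 15" as a secondary outcome.

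Section 14 describes the correlation analysis as concerning crSO2, "cFTOE and MAP in preterm and term infants at different time points, individually". Cardiac output does not appear in that section. A p-value below 0.05 counts as significant. On comparing the correlations, it says: "Comparison of correlation analyses at different time points and in term and preterm neonates will be descriptive". The between-group tests it names (chi-square, t-test, Mann-Whitney) compare characteristics and continuous variables, not correlations.

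Section 5 gives the number available per group: "If 50 infants are included and a drop-out rate of 10% is considered, 45 infants can be analyzed". Its precision figures are for one correlation within one group. Section 6 calls the study an observational pilot.

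**The concern.** A statement that one group's correlation is stronger than another's concerns a difference between two coefficients. The plan would put such coefficients side by side, and strictly it promises even those for MAP only. It attaches no uncertainty to the gap between them.

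The one inferential tool on offer is a p-value for each coefficient separately. That invites a familiar misreading: significant in preterm, not significant in term, therefore different. Two groups with the same underlying correlation will often split in this way by chance, and a gap that looks large at this sample size can be compatible with no difference. What is at stake is the support claimed for the second clause of Hypothesis II. Primary Hypothesis I does not rank the groups and is not affected.

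**Working it through.** **Inputs.** n = 45 per group (section 5: 50 less 10%). Threshold 0.05 (section 14), taken as two-sided because the section does not say. The documents give no cardiac-output correlation, so every r below is an assumption.

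**The plan's own figures.** Section 5 gives lower 95% limits of 0.14, 0.20, 0.26 and 0.32 for r = 0.40, 0.45, 0.50 and 0.55. The formula tanh(atanh(r) − 1.96/√(n−3)) gives 0.12, 0.18, 0.24 and 0.31 at n = 45, and the printed values at n = 50. That mismatch is a separate matter and nothing here depends on it. The plan gives no figure for the preterm-term difference.

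**Precision of the difference.** The groups are independent. With the usual Spearman variance of 1.06/(n−3) on the Fisher-z scale:

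- SE of the difference = √(1.06/42 + 1.06/42) = 0.2247.
- 95% half-width = 1.96 × 0.2247 = 0.440.
- On the raw scale at r = 0.40 in both groups: 0.440 × (1 − 0.40²) = 0.370.
- If only 35 or 30 infants per group had usable pairs (assumed), the z half-width would be 0.504 or 0.549.

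**Illustration.** Suppose 0.40 is observed in preterm and 0.10 in term neonates.

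- z difference = 0.4236 − 0.1003 = 0.323; 95% CI 0.323 ± 0.440 = −0.117 to 0.764 from unrounded values.
- Raw difference 0.30. The single-group limits are 0.112 to 0.626 and −0.208 to 0.390. Combining them gives a lower limit of 0.30 − √((0.40−0.112)² + (0.390−0.10)²) = −0.109 and an upper limit of 0.30 + √((0.626−0.40)² + (0.10+0.208)²) = 0.682.

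So a fourfold ratio of observed coefficients is compatible with no difference.

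**How often separate p-values disagree when the truth is equal.** Let p be the chance that one group reaches p<0.05. Exactly one of two independent groups does so with probability 2p(1−p). The SE of a single z is √(1.06/42) = 0.1589, and p is approximately Φ(atanh(r)/0.1589 − 1.96), plus a negligible opposite tail.

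| True r in both groups (assumed) | p | Exactly one group significant |
|---|---|---|
| 0.20 | 0.25 | 37% |
| 0.30 | 0.50 | 50% |
| 0.40 | 0.76 | 36% |

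Simulating Spearman coefficients from bivariate normal data gave 38%, 50% and 35%. With equal group sizes, half of these splits would favour preterm, the direction hypothesised.

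**What the interval could show.** Chance that it excludes zero with 45 per group, from Φ(Δz/0.2247 − 1.96) plus the small opposite tail:

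| True r, preterm vs term (assumed) | Δz | Chance |
|---|---|---|
| 0.40 vs 0.19 | 0.231 | 18% |
| 0.40 vs 0.10 | 0.323 | 30% |
| 0.40 vs 0 | 0.424 | 47% |
| 0.55 vs 0 | 0.618 | 79% |

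The 0.19 borrows the size of the blood-pressure value for preterm infants in section 5, only to show a small gap. It is neither a cardiac-output nor a term value.

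**The case against.** The strongest reply is that the plan openly declares the comparison descriptive, in a study that section 6 calls a pilot, and that the preterm clause is only the subordinate part of a secondary hypothesis. All of that stands, and it limits the weight of the point. It does not remove it. An interval is compatible with a descriptive aim, and the pilot label does not explain why section 14 leaves out cardiac output.

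A second reply is that the intervals will be wide and that there would be six of them. That also stands. If the six were independent, the chance that at least one excluded zero with no true difference would be 1 − 0.95⁶ = 26%. They must therefore be labelled exploratory and unadjusted.

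A third reply is that a correlation depends on the spread of both variables. The preterm group is everyone below 37+0 weeks, and no indexing of cardiac output to weight is stated. A difference in correlations could partly reflect different spread, and the interval covers sampling error only. This is correct, and the plan should say so.

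Three stronger readings might tempt a reader.

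- That cardiac output will not be captured, because section 13 does not list it. Section 7.2 says that "NIRS measurements, non-invasive blood pressure and cardiac output" will be recorded, and the section 13 list also omits the respiratory-function monitoring of section 7.1, so it does not look exhaustive.
- That the two groups might receive different coefficients, because section 14 says "Correlations will be performed using Spearman's rank correlation coefficient or Pearson's correlation when appropriate". Nothing there says the groups will be treated differently, and section 5 plans on Spearman. Both this and the previous item are minor wording matters.
- That a formal, powered test is missing. The plan never promises one.

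**Conclusion.** The point holds as a modest improvement to the secondary analysis. No section plans a cardiac-output correlation, or an estimate or interval for the preterm-term difference that section 3.2 expects. The only inferential rule offered would split the groups by chance in about 36% to 50% of studies if both had the same true correlation of 0.20, 0.30 or 0.40. Those percentages rest on assumed correlations, 45 analysable infants per group, a two-sided 0.05 threshold and the Fisher-z approximation. The half-width of 0.44 on the z scale needs only the sample size and the Spearman variance formula.

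A reader might infer that the primary analysis is flawed, or that a descriptive comparison is wrong in itself. The documents support neither. Hypothesis I makes no group ranking, and a declared descriptive comparison is acceptable in a pilot. The comparison across time points can stay descriptive.

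**What to change.** Change section 14 as follows.

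1. Add Spearman correlations of cardiac output with crSO2 and with cFTOE at minutes 5, 10 and 15 in each group, each with a 95% CI.
2. For these correlations, report the preterm-minus-term difference with its 95% CI: Fisher-z difference, SE = √(1.06/(n₁−3) + 1.06/(n₂−3)), where n₁ and n₂ are the infants in each group with both measurements at that minute. Label it exploratory and unadjusted for multiplicity. State that stronger means more positive for crSO2 and more negative for cFTOE, in line with section 3.2.
3. State that a group difference will not be inferred from one p-value falling below 0.05 and the other above it.
4. State that the difference may partly reflect different spread of cardiac output or oxygenation in the two groups, which the interval does not cover.

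The cost is a few sentences, 12 within-group coefficients (two outcomes, three minutes, two groups) and six difference intervals. No extra infants or measurements are needed. The drawback is that the intervals will often be inconclusive, and the report should say so.
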